#### **3.2.2 Radiographic Progression**

Radiographic progression will be evaluated by Response Evaluation Criteria in Solid Tumors (RECIST) version 1.1 criteria, with definitions of CR, PR, SD, and PD for target and non-target lesions as defined below. Baseline imaging defined as the CT and bone scan obtained prior to starting treatment. All baseline evaluations should be performed as closely as possible to the beginning of treatment and never more than 6 weeks before the beginning of the treatment.

Lesions are categorized as either measurable or non-measurable based on the criteria below. All measurements should be taken and recorded in metric notation using a ruler or calipers. Tumor lesions

## Mount Sinai The Tisch Cancer Institute

that are situated in a previously irradiated area will not be considered measurable. The same method of assessment and the same technique should be used to characterize each identified and reported lesion at baseline and during follow-up.

### *Target Lesions*

All measurable lesions up to a maximum of 5 lesions per organ and 10 lesions in total, representative of all involved organs, should be identified as target lesions and recorded and measured at baseline. Target lesions should be selected on the basis of their size (lesions with the longest diameter) and their suitability for accurate repeated measurements (either by imaging techniques or clinically). A sum of the longest diameters (LD) for all target lesions will be calculated and reported as the baseline sum LD. The baseline sum LD will be used as reference by which to characterize objective tumor response.

### *Non-Target Lesions*

All other lesions (or sites of disease) should be identified as non-target lesions and should also be recorded at baseline. Non-target lesions include measurable lesions that exceed the maximum numbers per organ or total of all involved organs as well as non-measurable lesions. Measurements of these lesions are not required, but the presence or absence of each should be noted throughout follow-up.

#### **3.2.2.1 Response Criteria for Target Lesions**

*Complete Response (CR):* Disappearance of all target lesions. Any pathological lymph nodes (whether target or non-target) must have reduction in short axis to <10 mm.

*Partial Response (PR):* At least a 30% decrease in the sum of the longest diameter (LD) of target lesions, taking as reference the baseline sum LD.

*Progressive Disease (PD):* At least a 20% increase in the sum of the LD of target lesions, taking as reference the smallest sum LD recorded since the treatment started. The sum must also demonstrate an absolute increase of at least 5 mm. The appearance of one or more new lesions is also considered progression.

*Stable Disease (SD):* Neither sufficient shrinkage to qualify for PR nor sufficient increase to qualify for PD, taking as reference the smallest sum LD since the treatment started.

#### **3.2.2.3 Outcomes Based on Radionuclide Bone Scans**

The subjectivity in interpreting serial changes in radionuclide bone scan is well recognized. The primary outcome will be whether the scan is stable or improved vs. worse or with evidence of progression. Changes in intensity will not be used as an outcome measure.

**Stable/Improved:** A stable or improved classification requires that no new lesions appear or that new pain has not developed in an area that was previously visualized.

### **3.2.3 Safety**

Safety and tolerability of the combination of 5-AZA and ATRA will be assessed by the recording of adverse events, monitoring of vital signs and physical examinations, safety laboratory evaluations, and 12-lead ECG. Adverse events will be graded according to the Common Terminology Criteria for Adverse Events (CTCAE) version 4.03. This will be assessed at baseline examination and every 4 weeks.

## **3.3 Secondary Study Endpoints**

Secondary end points include time to tumor progression from start of treatment phase 1 and correlation of antitumor activity and tumor progression with levels of dormancy biomarkers.

### **3.3.1 Time to disease progression**

Time to disease progression is defined as a composite of either PSA or radiographic progression, whichever occurs first. Please refer to 3.2 for further details.

### **3.3.2 Dormancy biomarkers**

We will measure the dormancy biomarkers TGF $\beta$ 2, BMP7, BMP4, GAS6, retinoic acid, NR2F1, in BM and/or blood supernatants of our study patients. We will correlate the levels of these biomarkers with clinical response to treatment and disease progression.

## **4. ELIGIBILITY CRITERIA**

### **4.1 Patient Eligibility**

Eligibility waivers are not permitted. Subjects must meet all of the inclusion and must not meet any of the exclusion criteria to be registered to the study. Study treatment may not begin until a subject is registered.

#### **4.1.1 Inclusion Criteria**

- Histologically confirmed adenocarcinoma of the prostate
- Rising PSA
- PSADT  $\leq$  10 months prior to initiation of ADT
- No evidence of regional or active distant metastases, except for regional metastasis where salvage radiation therapy is not an option
- Indication for ADT after receiving definitive local therapy
- Males  $\geq$  18 years.
- ECOG performance status of  $\leq$  2
- Men must agree to use a condom and not father a child or donate sperm for the duration of the study and for 90 days after completion of therapy
- Ability to understand and the willingness to sign a written informed consent
- Ability to adhere to the study visit schedule and requirements of the protocol

#### **4.1.2 Exclusion Criteria**

- Patients who have received ADT and/or other chemotherapy within 3 months prior to entering the study.
- Patients who have had radiotherapy or surgery within 4 weeks prior to entering the study. Minimally-invasive procedures for the purpose of diagnosis or staging of the disease are permitted.
- Patients may not be receiving any other investigational agents.

- Patients with known brain metastases should be excluded from this clinical trial because of their poor prognosis and because they often develop progressive neurologic dysfunction that would confound the evaluation of neurologic and other adverse events.
- History of allergic reactions attributed to compounds of similar chemical or biologic composition to 5-AZA and ATRA.
- Uncontrolled intercurrent illness including, but not limited to, ongoing or active infection, symptomatic congestive heart failure, unstable angina pectoris, cardiac arrhythmia, or psychiatric illness/social situations that would limit compliance with study requirements.
- Significant active cardiac disease within the previous 6 months
- Inadequate organ and marrow function as defined below:

- leukocytes	$\leq$ 3,000/mcL
- absolute neutrophil count	$\leq$ 1,500/mcL
- platelets	$\leq$ 100,000/mcL
- total bilirubin	above normal institutional limits
- AST(SGOT)/ALT(SPGT)	$\geq$ 2.5 X institutional upper limit of normal
- creatinine	above normal institutional limits

#### **4.2 Pretreatment Evaluation**

All patients must sign a written informed consent form before study specific screening procedures are performed. Informed consents may be obtained up to 30 days prior to day 1 of study. Screening procedures to evaluate patient eligibility for the study will be conducted within 30 days prior to day 1. The pretreatment evaluation includes a complete medical history and physical examination, laboratory studies including complete blood count (CBC) with differential, comprehensive metabolic panel (CMP), lactate dehydrogenase (LDH), PSA, testosterone panel, and baseline EKG. A bone scan, and CT chest abdomen/pelvis will also be performed up to 60 days prior to Day 1 of treatment. 18F-Fluciclovine (Axumin) PET/CT may be substituted for pre-treatment CT chest/abdomen/pelvis and bone scan and can be obtained up to 60 days prior to Day 1 of treatment. If the patient meets eligibility, they will return on Day 1 for Leuprolide administration.

### **5. DRUG INFORMATION**

#### **5.1 5-azacitidine**

Please see product package insert for complete details.

##### **5.1.1 Availability**

5-azacitidine is commercially available

##### **5.1.2 Formulation**

5-azacitidine is available as a reconstituted suspension in vials containing 100 mg of 5-azacitidine. Commercial supplies of 5-azacitidine will be used for the study

##### **5.1.3 Storage, preparation, and administration**

Azacitidine is associated with a moderate emetic potential; antiemetics are recommended to prevent nausea and vomiting.

## Mount Sinai The Tisch Cancer Institute

**SubQ:** The manufacturer recommends equally dividing volumes >4 mL into 2 syringes and injecting into 2 separate sites; however, policies for maximum SubQ administration volume may vary by institution; interpatient variations may also apply. Rotate sites for each injection (thigh, abdomen, or upper arm). Administer subsequent injections at least 1 inch from previous injection sites; do not inject into tender, bruised, red, or hard areas. Allow refrigerated suspensions to come to room temperature (up to 30 minutes) prior to administration. Resuspend by inverting the syringe 2 to 3 times and then rolling the syringe between the palms for 30 seconds.

### 5.1.4 Mechanism of Action

Promotes hypomethylation of DNA to restore normal gene differentiation and proliferation.

### 5.1.5 Drug dosing rationale

The proposed dosing of 5-AZA is based on the FDA-approved doses for MDS. 5-AZA has been tested in phase II trials of PCa patients. Sonpavde et al conducted a phase II trial in 26 patients with CRPC and PSADT < 3 months. A dose of 40 mg/m^2 SQ on days 1-5 was administered every 28 days. The primary endpoint was prolongation of PSADT by greater than 3 months and was noted in 19 patients (55%). PSA declines were noted in 14 of 36 evaluable patients. Median PSADT was 2.8 months after treatment, compared with 1.5 months prior to starting (p<0.01).

5-azacitidine is generally well tolerated, as demonstrated by a phase II trial in chemo-naive castration-resistant metastatic prostate cancer. The toxicities were generally mild and manageable. In those patients with toxicities, the most common were fatigue (41.2%), constipation (41.2%), nausea (35.3%), injection site reaction (32.4%), vomiting (26.5%), anorexia (20.6%), anemia (20.6%), and neutropenia (17.6%). The most common grade 3 toxicities were fatigue (11.8%) and neutropenia (5.9%). There were no grade 4 toxicities. Only 4 out of 36 patients discontinued therapy due to toxicities.

### 5.1.6 Adverse Events

Incidence rates of adverse events associated with 5-azacitidine are provided in the product package insert. The most common adverse events treatment are listed below.

**Cardiovascular:** Peripheral edema (7% to 19%), chest pain (16%)

**Central nervous system:** Fatigue (13% to 36%), rigors (26%), headache (22%), dizziness (19%), anxiety (5% to 13%), depression (12%), malaise (11%), pain (11%), insomnia (9% to 11%)

**Dermatologic:** Erythema (7% to 17%), pallor (16%), skin lesion (15%), skin rash (10% to 14%), pruritus (12%), diaphoresis (11%)

**Endocrine & metabolic:** Weight loss (≤16%), pitting edema (15%), hypokalemia (6% to 13%)

**Gastrointestinal:** Nausea (48% to 71%), vomiting (27% to 54%), constipation (34% to 50%), diarrhea (36%), anorexia (13% to 21%), abdominal pain (11% to 16%), abdominal tenderness (12%)

**Hematologic & oncologic:** Thrombocytopenia (66% to 70%; grades 3/4: 58%), anemia (51% to 70%; grades 3/4: 14%), neutropenia (32% to 66%; grades 3/4: 61%), leukopenia (18% to 48%; grades 3/4: 15%), bruise (19% to 31%), petechia (11% to 24%), febrile neutropenia (14% to 16%; grades 3/4: 13%), bone marrow depression (nadir: days 10 to 17; recovery: days 28 to 31)

**Local:** Injection site reactions (14% to 29%): Erythema (35% to 43%; more common with IV administration), pain (19% to 23%; more common with IV administration), bruising (5% to 14%)

Neuromuscular & skeletal: Weakness (29%), arthralgia (22%), limb pain (20%), back pain (19%), myalgia (16%)

Respiratory: Cough (11% to 30%), dyspnea (5% to 29%), pharyngitis (20%), epistaxis (16%), nasopharyngitis (15%), upper respiratory infection (9% to 13%), pneumonia (11%), rales (9% to 11%)

Miscellaneous: Fever (30% to 52%)

## **5.2 All-trans retinoic acid**

Please see product package insert for complete details.

### **5.2.1 Availability**

ATRA is commercially available

### **5.2.2 Formulation**

ATRA is available as an oral capsule of 10 mg.

### **5.2.3 Storage, preparation, and administration**

Dosage calculations will be rounded to the nearest 10 mg increment and given in two divided doses per day.

ATRA will be taken orally with meals.

### **5.2.4 Mechanism of Action**

Promotes hypomethylation of DNA to restore normal gene differentiation and proliferation.

### **5.2.5 Drug dosing rationale**

The proposed dosing of ATRA is based on the FDA-approved doses for acute promyelocytic leukemia. ATRA has been studied in several phase II trials. Trump et al gave ATRA 50 mg/m^2 daily x 14 days every 3 weeks to 17 CRPC patients and saw no clinical responses. However, Kelly et al showed in a trial of ATRA 45 mg/m^2 daily combined with cis-retinoic acid + IFN that 4 patients with hormone-sensitive PCa had stabilization in PSA kinetics.

ATRA has been studied in multiple phase II trials of PCa patients. In both studies, the toxicities were mild and manageable. In the study by Trump et al., only one patient required a 50% dose reduction due to intolerable headaches occurring on day 1 of therapy. Most patients reported xeroderma, cheilosis, and mild conjunctivitis. Two men developed painful balanitis controlled with emollients. Six patients had headaches; two had mild and four had moderate headaches. No other important toxicities were noted. In the study by Kelly et al., only one patient required dose reduction, which was for fatigue. Xeroderma and chelitis were common adverse events, which were successfully treated with skin emollients. Other mild toxicities (grade 1 or 2) included elevated transaminases (79%), headaches (57%), constipation (50%), and nausea (29%). The most common hematologic toxicities were mild anemia and thrombocytopenia except for two patients, who had grade 3 anemia.

### 5.2.6 Adverse Events

Incidence rates of adverse events associated with ATRA are provided in the product package insert. The most common adverse events are listed below.

**Cardiovascular:** Peripheral edema (52%), chest discomfort (32%), edema (29%), cardiac arrhythmia (23%), flushing (23%), hypotension (14%), hypertension (11%), localized phlebitis (11%)

**Central nervous system:** Headache (86%), malaise (66%), shivering (63%), pain (37%), dizziness (20%), anxiety (17%), paresthesia (17%), depression (14%), insomnia (14%), confusion (11%)

**Dermatologic:** Xeroderma (≤77%), skin rash (54%), diaphoresis (20%), pruritus (20%), alopecia (14%), skin changes (14%)

**Endocrine & metabolic:** Hypercholesterolemia (≤60%), hypertriglyceridemia (≤60%), weight gain (23%), weight loss (17%)

**Gastrointestinal:** Dry mucous membranes (≤77%), nausea (≤57%), vomiting (≤57%), gastrointestinal hemorrhage (34%), abdominal pain (31%), mucositis (26%), diarrhea (23%), anorexia (17%), constipation (17%), dyspepsia (14%), abdominal distention (11%)

**Hematologic & oncologic:** Hemorrhage (60%), leukocytosis (40%), disseminated intravascular coagulation (26%)

**Hepatic:** Increased liver enzymes (50% to 60%)

**Infection:** Infection (58%)

**Neuromuscular & skeletal:** Ostealgia (77%), APL differentiation syndrome (≤25%), myalgia (14%)

**Ophthalmic:** Eye disease (17%), visual disturbance (17%)

**Otic:** Oticgia (23%; ear fullness)

**Renal:** Renal insufficiency (11%)

**Respiratory:** Upper respiratory complaint (63%), dyspnea (60%), respiratory insufficiency (26%), pleural effusion (20%), pneumonia (14%), rales (14%), wheezing (expiratory: 14%)

**Miscellaneous:** Fever (83%)

### 5.2.7 Drug-drug interactions

ATRA is a major CYP2C8 substrate:

**CYP2C8 Inducers (Strong):** May increase the metabolism of CYP2C8 Substrates (High risk with Inducers). Management: Consider an alternative for one of the interacting drugs. Some combinations may be specifically contraindicated. Consult appropriate manufacturer labeling.

**CYP2C8 Inhibitors (Moderate):** May decrease the metabolism of CYP2C8 Substrates (High risk with Inhibitors).

Management: Monitor during therapy.

**CYP2C8 Inhibitors (Strong):** May decrease the metabolism of CYP2C8 Substrates (High risk with Inhibitors).

Management: Consider an alternative for one of the interacting drugs. Some combinations may be specifically contraindicated. Consult appropriate manufacturer labeling.

**Table 1. Therapeutic agents: Dosing and administration schedule**

Agent	Dose	Route	Schedule	Cycle Length
5-AZA	40 mg/m 	SQ	Days 1-5 x 12 weeks	4 weeks (28 days)
ATRA	45 mg/m  daily (divided into 2 doses)	PO	Days 3-7 x 12 weeks	

*Note: Height and weight will be obtained at Day 1 of each treatment cycle to determine treatment dosing.*

The daily dosing for ATRA will be rounded to the nearest 10 mg increment and given in two divided doses per day.

**Table 2. Administration schedule per cycle**

Drug	Cycle							
	D1	D2	D3	D4	D5	D6	D7	D8-28
5-AZA	X	X	X	X	X			
ATRA			X	X	X	X	X	

The treatment schedule maybe adjusted for up to 7 days if any scheduling conflicts related to patient availability and/or holidays.

## 6. ADVERSE EVENTS

An adverse event or experience is defined as any symptom, sign, illness, or untoward experience (including a clinically significant laboratory finding classified as grade  $\geq 3$  by the National Cancer Institute's Common Terminology Criteria for Adverse Events [CTCAE] that develops or worsens during the study, whether the event is considered related to study drug, and should be recorded only after the first dose of study drug is taken. Serious adverse events are recorded from the time the informed consent form is signed.

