#### STUDY SUMMARY

Title	A pilot study of the combination of 5-azacitidine (5-AZA) and all-trans retinoic acid (ATRA) for prostate cancer with PSA-only recurrence
Short Title	Prostate Cancer Dormancy
Protocol Number	
Phase	Pilot, phase 2
Methodology	Randomized, open label
Study Center(s)	Single-center
Objectives	
Primary
 

1) Evaluate disease progression-free rate at the end of Treatment Phase 1 between 5-AZA+ATRA and no-therapy.

2) Assess safety of the 5-AZA and ATRA combination therapy

 
Secondary:
 

1) Evaluate time to disease progression from start of Treatment Phase 1

2) Correlate antitumor activity and disease progression with biomarkers of dormancy in BM aspirates and peripheral blood

Number of Subjects	20 evaluable patients; the target accrual number is set at 30 to account for screen failures.

Diagnosis and Eligibility Criteria	
Diagnosis: Histologically confirmed adenocarcinoma of the prostate
 
Main inclusion criteria: 1) Rising PSA 2) PSADT <math>\leq</math> 10 months prior to initiation of ADT 2) 3) Received definitive local treatment 4) Indication for ADT 5) No evidence of regional or active distant metastases, except for regional metastases where salvage radiation therapy is not an option
 
Main exclusion criteria: 1) Patients who have received ADT and/or other chemotherapy within 3 months prior to entering the study. 2) Patients who have had radiotherapy or surgery within 4 weeks prior to entering the study. Minimally-invasive procedures for the purpose of diagnosis or staging of the disease are permitted.

Study Product(s), Dose, Route, Regimen	5-azacitidine: 40 mg/m  SQ on days 1-5 All-trans retinoic acid: 45 mg/m  PO daily (divided into 2 doses) on days 3-7 One cycle of treatment: 28 days
Duration of administration	Drugs will be administered on a 28-day cycle
Reference therapy	No reference therapy
Statistical Methodology	We will compare the disease progression-free rate at end of treatment phase 1 and time to disease progression from start of Treatment Phase 1 between 5-AZA+ATRA and no-therapy. Descriptive summary will be provided for safety endpoints and dormancy marker panel. The effect of biomarker abundance on recurrence free survival will be determined using Kaplan-Meier curves stratified across biomarker abundance groups.
Estimated enrollment period	12

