Currently, patients who have received definitive local treatment with either RT or surgery undergo serial measurements of PSA to detect early disease recurrence. Such monitoring leads to the identification of men with PSA-only (biochemical) recurrence without evidence of clinical symptoms, or radiographic evidence of recurrent or disseminated disease. Androgen deprivation therapy (ADT) is the standard of care for the initial systemic therapy, however the optimal timing for initiation of ADT remains controversial due to paucity of clinical trial data in this population. Furthermore, ADT causes side effects such as hot flashes, loss of libido, decreased muscle mass, fatigue, and osteoporosis, which can significantly lower the quality of life in otherwise asymptomatic men.

Leuprolide is considered standard of care for prostate cancer with PSA-only recurrence. One dose of Leuprolide has a transient effect of decreasing PSA to negligible levels resulting in a similar baseline for

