## 3. STUDY DESIGN

### **3.1 General Design**

This is a prospective, open-label, randomized, pilot study of reprogramming therapy in patients with recurrent PCa based on rising PSA only. Reprogramming therapy will include 5-azacitidine and all-trans retinoic acid. Expected duration of subject participation is 24 months.

All study will be assigned in a 1:1 randomization using computer random number generator to either the '5-AZA+ATRA' group or the 'no therapy' group. All enrollees will receive Leuprolide 7.5 mg x 1 on Day 1. On Day 29, they will initiate treatment phase 1. During this phase, patients in the '5-AZA + ATRA' group will receive treatment on a 28-day cycle, in the absence of prohibitive toxicities, for 3 cycles. During treatment phase 2, the 'no therapy' group will receive 5-AZA + ATRA on a 28-day cycle, in the absence of prohibitive toxicities, for 3 cycles. The treatment effect will be determined via comparing the intra-individual disease progression outcome at the end of the treatment phase 1, with period effect being separated through randomization. After treatment phase 1 and phase 2, all patients will be followed for a total of 24 months from the start of the study or until the events leading to discontinuation as outlined in Section 7.1 are observed. 5-AZA will be given subcutaneously on days 1-5 at a dose of 40 mg/m^2. ATRA, dosed at 45 mg/m^2 daily (divided into 2 doses), will be taken orally on days 3-7 of each cycle.

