### **8.4 Data analyses**

Analysis on efficacy and safety:

Patients will receive at least 8 weeks of treatment in order to be eligible for efficacy analysis. Patients who discontinued due to toxicity after 8 weeks of treatment will be included in efficacy analysis. Descriptive statistics such as mean/median/range and frequency will be provided for continuous and categorical variables separately, and the distributions of period baseline variables are contrasted between 5-AZA+ATRA and placebo using Wilcoxon statistics and Fisher's exact test statistics for continuous and categorical variables separately. Waterfall plot will be provided for PSA change relative to period baseline for all patients for each treatment arm and period. Analysis will follow the two-step procedure prescribed in for randomized crossover study for binary endpoint. To test for carryover effect, Wilcoxon rank-sum test stratified by prior PSADT will be performed to assess whether the sum of outcome variables from both periods is different between the randomization arms. If the test yields insignificant results, a similar test will be performed to compare the within-patient outcome difference between period 1 and 2 between the randomization arms to assess the treatment effect. If the carryover effect is significant, the primary analysis will be based on the progression free rates at the end of first treatment period using Chi-square test. In addition, general linear mixed model will be applied to assess the treatment effect, carryover effect, and period effect, adjusting for the stratification factor prior PSADT. The time to disease progression is defined as time to either PSA progression or radiographic progression whichever occurs first since discontinuation of ADT. Time to event endpoints will be summarized using Kaplan-Meier method. The time to event endpoints will be estimated using rank preserving failure time model (RPFTM) to obtain the counter-factual event times assuming cross-over did not occur (R package "rpfstm").

Descriptive summary will be provided for the safety endpoints. All patients who received at least one dose of study drug (treated set) will be included in the safety analysis.

Correlative analysis and biomarkers:

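### Section 6 leaves non-serious adverse events unrecorded until the first dose of an undefined study drug, which conflicts with the scheduled AE monitoring and weakens interpretation of the co-primary safety objective

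*Combined protocol and SAP*

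**What the plan says.** **Recording rule.** Section 6 says that AEs "should be recorded only after the first dose of study drug is taken". The next sentence treats serious events differently: "Serious adverse events are recorded from the time the informed consent form is signed".

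**Study drug.** No section defines the term. In the study summary, the row "Study Product(s), Dose, Route, Regimen" names 5-azacitidine and ATRA and omits leuprolide. Section 3.1 describes the experimental treatment the same way: "Reprogramming therapy will include 5-azacitidine and all-trans retinoic acid". Section 6.2.2 uses the term when it sets out holds of 5-AZA and ATRA, and the medication diary described after Table 7 covers those two agents. Leuprolide appears separately in section 3.1: "All enrollees will receive Leuprolide 7.5 mg x 1 on Day 1".

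**Assessment schedule.** Section 3.2.3 lists AEs, vital signs, examinations, laboratory tests and ECG, and adds: "This will be assessed at baseline examination and every 4 weeks". Section 7 has AEs and laboratory values assessed at the start of each cycle. Table 8 lists AE monitoring every four weeks in the treatment phases. None of these entries is restricted to one arm.

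**Analysis.** Section 8.4 plans a descriptive safety summary and fixes its population: "All patients who received at least one dose of study drug (treated set) will be included in the safety analysis". It plans no split by arm or period.

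**The concern.** Safety of the combination is one of two co-primary objectives (section 2.1). Every patient receives leuprolide four weeks before Treatment Phase 1, so some symptoms seen on 5-AZA + ATRA may come from androgen deprivation. The protocol gives an example. Section 1.2 states that "ADT causes side effects such as hot flashes, loss of libido, decreased muscle mass, fatigue, and osteoporosis", and section 5.1.5 reports fatigue as one of the two most common azacitidine toxicities in the cited phase II trial (41.2% overall, 11.8% at grade 3).

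The no-therapy arm in Phase 1 has had leuprolide but neither study product, and it is followed at the same time as the treated arm. It is therefore the natural reference for how often such symptoms occur anyway. Most will be non-serious, so serious-event reporting does not replace it. The lead-in matters for a related reason: section 6 counts events that develop or worsen, and a symptom that began after leuprolide and carried into cycle 1 would have no recorded onset.

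The sections also give sites opposing instructions. For a Phase 1 control, staff cannot both assess AEs every four weeks and leave non-serious AEs unrecorded until Phase 2.

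**Working it through.** The plan states no figure on this point, so there is none to reproduce. The check is a reading of the sections followed by a count of patient-time.

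**1. What starts the recording.** If study drug means 5-AZA/ATRA, recording of non-serious AEs starts at Day 29 in the drug-first arm and at the start of Phase 2 in the other arm. If leuprolide counts, it starts at Day 1 in both. The first reading fits the summary row, section 6.2.2 and the diary.

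**2. Timeline.** The lead-in is Days 1–28 (4 weeks). Phase 1 is 3 × 28 = 84 days, Days 29–112 (12 weeks). Phase 2 starts on Day 113 if it follows directly; the documents state no gap, so this is an assumption.

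**3. Patient-weeks under the literal rule.** Inputs: 20 evaluable patients (study summary) and 1:1 allocation (section 3.1), so about 10 per arm, all assumed to complete both phases.

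| Period | Drug-first arm | No-therapy-first arm |
|---|---|---|
| Lead-in, 4 weeks | 10 × 4 = 40, not recorded | 10 × 4 = 40, not recorded |
| Phase 1, 12 weeks | 10 × 12 = 120 on drug, recorded | 10 × 12 = 120 untreated, not recorded |
| Phase 2, 12 weeks | 10 × 12 = 120 off drug, recorded | 10 × 12 = 120 on drug, recorded |

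Unrecorded: 40 + 40 + 120 = 200. Recorded on drug: 120 + 120 = 240. Total: 20 × 28 = 560. The unrecorded share is 200/560 = 36%, and it contains all the time before any patient meets 5-AZA or ATRA. The drug-first arm's off-drug time in Phase 2 is recorded but follows exposure, so it is not a clean background.

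**4. The conflict.** Sections 3.2.3 and 7 and Table 8 call for AE assessment in Phase 1 without an arm restriction. Table 8 does restrict by treatment where that is meant: its footnote on extra blood counts applies only to patients on 5-AZA. The AE row has no such footnote. For the lead-in, the conflict rests mainly on the baseline and four-weekly wording of section 3.2.3, since Table 8 has no lead-in column.

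**5. What full recording would buy.** With n = 10 per arm, two-sided 10% level and a normal approximation, power = Φ{[|p1 − p0| − 1.645√(2p̄(1 − p̄)/n)] / √[(p0(1 − p0) + p1(1 − p1))/n]}. The rates are illustrative assumptions.

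- 10% vs 40%: (0.30 − 1.645 × 0.194)/0.182 ≈ −0.10, power about 46%.
- 20% vs 50%: (0.30 − 1.645 × 0.213)/0.202 ≈ −0.25, power about 40%.

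The gain is in interpretation, not in a test.

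**The case against.** The strongest reply is that little is lost. Serious AEs are recorded from consent, and vital signs, examinations, blood counts and chemistry are scheduled every four weeks in both arms. A reader might infer that controls supply no safety data in Phase 1; the documents contradict that. This part of the reply stands and confines the point to non-serious AEs.

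The reply continues that the safety objective is to assess, not compare. Comparison appears only in the efficacy objectives, the safety analysis is descriptive, and the stopping rule in section 6.2 counts toxicity in the treatment window and four weeks beyond. A reader might infer that a planned randomised safety comparison has been lost. None was planned, so that inference fails too.

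Third, leuprolide effects may still be partly distinguishable. Of the eight common azacitidine toxicities in section 5.1.5, only fatigue is on the section 1.2 list, and that list concerns androgen deprivation generally rather than one leuprolide dose. Investigators judge relatedness for grade 3–4 non-haematological events. Controls start the combination about 16 weeks after leuprolide rather than 4, which gives an indirect contrast. It would therefore be too strong to say that the two sources cannot be separated.

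Finally, study drug is undefined, and section 4.2 times imaging to the first day of treatment and then brings patients back on Day 1 for leuprolide, which leaves room for a wider meaning. If the visit schedule governs, the data may be collected after all. That makes the loss conditional, but it does not rescue the text: the two instructions still differ, and the same undefined term also sets the safety population in section 8.4.

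**Conclusion.** The point holds in limited form. Followed literally, section 6 leaves non-serious AEs unrecorded for about 120 control patient-weeks in Phase 1 and about 80 patient-weeks of lead-in, and it conflicts with the AE monitoring scheduled elsewhere. This removes the only concurrent, drug-naive background for events such as fatigue. A control who leaves before Phase 2 would also fall outside the treated set, so even his serious events would be absent from the planned safety summary.

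The consequence is a weaker interpretation of a descriptive co-primary objective, not an uninterpretable one. The count assumes 10 patients per arm, no early withdrawal, Phase 2 directly after Phase 1, and study drug meaning 5-AZA/ATRA. A reader might want to put a number on how far fatigue would be over-attributed to the combination. The documents give no rate for leuprolide alone, so no such figure is supported.

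**What to change.** 1. Define study drug once, and state whether leuprolide is included for AE recording and for the treated set.
2. Amend section 6 so that all AEs, serious or not, are recorded in both arms from Day 1, in line with section 3.2.3, section 7 and Table 8. Show the lead-in in Table 8.
3. In section 8.4, keep the treated-set summary and add a descriptive AE table covering all randomised patients, by randomised arm and period (lead-in, Phase 1, Phase 2).

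The cost is some wording, one table and slightly more AE data entry at visits that already take place. Section 8.4 should say that, with about 10 patients per arm, the new table is descriptive and no test is intended.
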